1. LIST OF ABBREVIATIONS

ACT	Artemisinin-based combination therapy
AE	Adverse event
A/L	Artemether-lumefantrine
AQ	Amodiaquine
CNM	National Center for Parasitology, Entomology and Malaria Control
CRF	Case record form
CTSG	Clinical Trials Support Group (MORU)
DHA	Dihydroartemisinin
DNA	Deoxyribonucleic Acid
EDC	Electronic data capture
EDTA	Ethylene-diamine-tetra-acetic acid
G6PD	Glucose-6-phosphate dehydrogenase
GCP	Good Clinical Practice
GPS	Global Positioning System
Hb	Haemoglobin
Hct	Haematocrit
IRS	Indoor residual spraying
LLIN	Long-lasting insecticide treated bednets
MDR1	Multi-Drug Resistance Gene 1
MQ	Mefloquine
MORU	Mahidol-Oxford Research Unit
NMCP	National Malaria Control Programme
PA	Pyronaridine-artesunate
PAL	Prophylaxis with artemether-lumefantrine study
PCR	Polymerase Chain Reaction
QA	Quality Assurance
QC	Quality Control
SAE	Serious Adverse Event
SNP	Single-nucleotide polymorphism
SOP	Standard Operating Procedure
WHO	World Health Organisation
WWARN	Worldwide Antimalarial Resistance Network

2. SYNOPSIS

Study Title	An open-label individually randomised controlled trial to assess the efficacy of artemether-lumefantrine prophylaxis for malaria among forest goers in Cambodia
ACRONYM	PAL-Cambodia
Trial Design	An open-label randomised trial comparing the ACT artemether-lumefantrine (Coartem) with a multivitamin preparation, evaluating efficacy in preventing malaria among forest goers
Trial Participants	People planning to travel the forest within the next 72 hours in areas at high risk for malaria
Sample size	4400 participant episodes, with half allocated to each study arm
Inclusion Criteria	
 • Male or female, aged between 16 and 65 years • Planning to travel to the forest within the next 72 hours and stay overnight • Written informed consent • Willingness and ability of the participants to comply with the study protocol for the duration of the study
Exclusion Criteria	
 • For females: known pregnancy or breast feeding • Participants who have received artemisinin or a derivative or an artemisinin-containing combination therapy (ACT) within the previous 7 days • History of allergy or known contraindication to artemisinins, lumefantrine or multivitamins • Documented or claimed history of cardiac conduction problems. • Severe vomiting or diarrhoea • Signs/symptoms of clinical malaria (febrile or history of fever in the previous 24hours) confirmed by RDT
Planned Trial Period	12 months (September 2019 – July 2020) enrolment
Primary Objective	To compare the efficacy of the ACT artemether-lumefantrine versus a multivitamin preparation as defined by the 28-day PCR parasite positivity rate and incidence of confirmed clinical malaria of any species.
Secondary Objectives	
 1. To compare the efficacy of the ACT artemether-lumefantrine versus a multivitamin preparation as defined by the 28-day, 56-day and 84-day PCR parasite positivity rate and incidence of confirmed clinical malaria for each species. 2. To quantify the impact of the ACT artemether-lumefantrine as prophylaxis for forest goers on overall malaria transmission using mathematical modelling.

	
 3. To assess the impact of artemether-lumefantrine prophylaxis on the spread of genetic markers of artemisinin (such as Kelch13 mutations) and partner drug resistance. 4. To obtain data on the place of residence, work, recent travel history and risk behaviours of forest goers in order to improve the understanding of high risk groups, locations of malaria transmission and possible routes spread of malaria and artemisinin resistance. 5. To explore the duration, location and purpose of individual forest visits. 6. To obtain detailed data and GPS mapping on a subset of participants and their peers relating to the behaviours and risk factors associated with malaria infection in order to improve understanding of local malaria transmission among forest goers. 7. To determine the prevalence of asymptomatic Plasmodium infections in high risk populations at varying seasonal time points. 8. To determine the prevalence of other infectious diseases that affect the study population.
Primary endpoints	
 1. 28-day PCR Plasmodium positivity rate of any species 2. Proportion of participants with confirmed clinical malaria of any species reported between day 0 and day 28
Secondary endpoints	
 1. 28-day, 56-day and 84-day PCR Plasmodium positivity rate for each species 2. Proportion of participants with confirmed malaria reported between day 0 and day 28 for each species 3. Description of epidemiological situation of malaria in the study areas from passive surveillance data. 4. Prevalence of Kelch13 mutations and other genetic markers of antimalarial drug resistance of known functional significance. 5. Incidence of adverse events and serious adverse events by study arms during the course of prophylaxis. 6. Data on the place of residence, work, recent travel history and mobile phone use. 7. Detailed data and GPS mapping on a subset of participants and their peers relating to the behaviours and risk factors associated with malaria infection. 8. Overall prevalence of Plasmodium at baseline, stratified by season and risk factors. 9. 0, 28, 56 and 84-day capillary blood levels of lumefantrine. 10. Prevalence of serological diagnostic markers of other infectious diseases.
Drugs (See Appendix 2 for dosing regimens)	
Artemether-lumefantrine for 3 days followed by 2 doses weekly.
 
VERSUS
 
Multivitamin 3 days followed by 2 doses weekly.

3. BACKGROUND AND RATIONALE

In the Greater Mekong Subregion (GMS) adults are at highest risk for malaria. The most relevant disease vectors bite during daytime and outdoors which makes forest work a high-risk activity for malaria. The absence of effective vector control strategies and limited periods of exposure during forest visits suggest that chemoprophylaxis could be an appropriate strategy to protect forest workers against malaria.

3.1 Background

In the Greater Mekong Subregion (GMS) a large proportion of malaria transmission occurs in forested areas, which serve as perpetual sources of transmission [1-5]. Studies have demonstrated increased risk of malaria among forest goers, particularly in men of working age [6, 7] although these have largely been restricted to small geographical areas. Protecting forest goers from *Plasmodium* infections would not only benefit them directly but also people residing around their home. Malaria elimination efforts which do not consider the reinfection risk from forest workers are unlikely to succeed. However, preventing infections in forest workers is a major challenge. The biting rhythm and resting behaviour of *Anopheles dirus* reduces the impact of the two most commonly employed control measures, long-lasting insecticide treated bednets (LLIN) and indoor residual spraying (IRS). Several studies have also demonstrated poor use of personal protection measures against malaria transmission [8-10]. Two factors that increase malaria risk among forest workers are the basic character of overnight forest accommodation [9] and exposure to the *Anopheles* vectors (e.g. *An. dirus*), which tend to bite outdoors in daytime. LLIN have a high protective efficacy against nocturnal, indoor malaria transmission [11] but are less protective against daytime, outdoor-biting vectors like *An. dirus*. The improvised housing of forest workers is frequently poorly suited to hanging bed nets.[12] Imaginative interventions such as supplying forest workers with insecticide treated hammocks do not address the biting rhythm and resting behaviour of the vectors and have a disappointing uptake in field studies.[10, 12] In the absence of simple, effective, and affordable vector control interventions, providing forest goers with effective antimalarial prophylaxis seems a promising alternative approach to protect them against malaria.[13]

We propose to evaluate the feasibility and protective efficacy of antimalarial prophylaxis during forest work. It has been demonstrated in sub-Saharan Africa that chemoprophylaxis (SMC) of children, the highest risk group for malaria in tropical Africa, can reduce malaria cases by 75%, is cost effective and safe and can be given by community health workers [14, 15]. We propose to provide chemoprophylaxis to forest workers, the population group with the highest malaria risk in the GMS. In the proposed study we compare chemoprophylaxis with an antimalarial drug, artemether-lumefantrine (AL). A recent mass drug administration in Cambodia demonstrated that DHA/piperaquine remains effective to clear low-density, subclinical *P. falciparum* infections, but there are increasing treatment failures of clinical malaria cases [16] and markers of resistance to piperaquine in Cambodia are increasing. Although artesunate-pyronaridine has recently been introduced for treatment in parts of Cambodia, there are unresolved concerns about potential liver toxicity[17]. Evidence to date suggests that efficacy of artemether-lumefantrine remains high in Cambodia and is very well tolerated with an excellent toxicity profile and is thus the preferred potential option for prophylaxis by the National Malaria Control Programme. However, it must be taken with fat to maximize absorption. Previously it has been difficult or impossible to detect very low-density *Plasmodium* infections. The availability of more sensitive PCR methods allows us to detect *Plasmodium* infections with much lower densities [18, 19]. By use of PCR, we will be able to detect a difference in the prevalence of low density, subclinical *P. falciparum* infections between the two study arms in a relatively small sample of study participants.

3.2 Study Rationale

Chemoprophylaxis of forest workers could protect this high-risk group and could reduce or even interrupt transmission in villages. The highly encouraging results of seasonal malaria chemoprophylaxis (SMC) in selected regions of sub-Saharan Africa provide hope that targeting another high-risk group, forest workers, could reduce malaria transmission in Cambodia and the wider GMS. In sub-Saharan Africa, children remain the main risk group for *Plasmodium* infections. In SE Asia the main risk group are adults working and sleeping outdoors hence we propose to provide chemoprophylaxis for these adults. A major challenge for this strategy is the choice of an

appropriate chemoprophylactic regimen in the GMS. The chemoprophylactic regimen of choice in Africa is sulfadoxine/pyrimethamine (S/P) plus amodiaquine despite high level resistance against the S/P component of the regimen. Similarly, we propose the use of AL, a drug whose efficacy remains high in the GMS, unlike, for example DHA/piperaquine [20]. The proposed study will help to assess the efficacy and feasibility of prophylaxis to prevent malaria in forest workers, help to identify the optimal regimen, and predict its efficacy in reducing overall transmission. The proposed study is a critical step for future use of chemoprophylaxis to protect forest workers in the GMS against malaria.

3.3 Proposed activities

Artemether-lumefantrine prophylaxis trial

The study of AL versus a multivitamin will be a two-arm randomised open label comparative study. Laboratory assessments of malaria infection at baseline and day 28 post forest will be performed blind to treatment allocation and incidence of clinical cases during follow-up will be recorded.

Activities/outcomes

The main activity proposed is an *in vivo* clinical assessment of prophylaxis to prevent malaria in 4400 participant episodes in 50 villages in Stung Treng and Pursat Provinces, Cambodia. The subjects will be randomized in a one-to-one ratio between the ACT AL and a multivitamin preparation with no antimalarial activity.

The study sites have been chosen based on current information on incidence of malaria, known predominance of malaria among forest goers, presence of an established clinical research programme and feasibility to perform the proposed research activities.

Efficacy of AL ACT will be assessed through follow up visits 28 days (+/-7 days) after returning from the forest upon completing each course of prophylaxis when temperature, symptom questionnaires, brief physical examinations, and malaria parasite PCR, and, in selected individuals, parasite genetics will be performed. Episodes of confirmed clinical malaria among study participants at any time point between enrolment and follow-up will also be recorded.

All the organisations in this collaboration will work closely with local counterparts including the National Malaria Control Programmes (NMCPs), non-governmental and other relevant organisations. Training is an integral part of this collaborative working relationship, and the building of local research capacity is an essential component of all research plans.

All research-related activities, from study design, planning, implementation through to analysis and writing of reports will be performed jointly with local counterparts. Both on-the-job training and formal training will be provided when needed, in particular for Good Clinical Practice (GCP) skills.

The close interaction between WHO and its regional offices will ensure that new knowledge is disseminated efficiently and effectively throughout the region.

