5.4 Primary and secondary endpoints

5.4.1. Co-primary Endpoints

1. 28-day PCR positivity rate of *Plasmodium* infections of any species.
2. Proportion of participants with confirmed clinical malaria of any species reported between day 0 and day 28

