6. PROCEDURES

Study procedures will be performed according to the schedule of assessments (Appendix 1). This will require that participants are followed up every 28 days for up to 3 periods upon completion of a course of prophylaxis.

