6.6. Follow-up

Participants will be asked to return for a follow-up assessment any time from 28 to 35 days after commencing prophylaxis. This will be regardless of the duration of their visit to the forest or the number of times they visited it in that period. At this assessment, they will be interviewed about how long they spent in the forest, where they went, why, who they travelled with and about risk factors for infection. Brief physical examinations, vital sign and symptom questionnaire will be performed. They will also be asked to report any diagnostic tests and/or treatment for malaria during the preceding 28-35 days.

Blood sampling at follow-up

At each follow-up visit, the following blood will be taken:

All individuals:

- Parasite PCR (Up to 1 ml).

- Dried blood spot for lumefantrine level (0.2 ml)

In those with confirmed clinical malaria at any time point between enrolment and follow-up:

- Dry blood blots (0.4 ml, 3 spots) collected on filter papers for:
 - o Parasite DNA genotyping for genetic markers of antimalarial resistance.
 - o Parasite whole genome sequencing and barcoding to identify geographical origin of parasites and compare genotypes to identify persistent infections.

In individuals who are planning to return again to the forest within the following 28 days after the follow up visit, they will be asked to continue their weekly prophylaxis according to the original treatment allocation on enrolment. They will then be asked to return for a second follow-up visit a further 28 to 35 days later when the above procedure will be repeated. This will be repeated one more time. If the person cannot be followed up within the scheduled period, e.g. because they do not return from the forest in time, then they will be followed up at the first opportunity and this will be recorded in the CRF.

Thus individuals may take prophylaxis continuously for a maximum of 3 periods of 28-35 days in the forest plus 4 weeks after returning totaling 112 days. The choice of study medication for each individual will follow the initial assignment on enrolment throughout the follow-up period.

In those who do not declare an intention to return to the forest within 28 days at any follow-up visit, no further follow-up visits will be offered at that time but they will be asked to complete 4 weeks of prophylaxis following their last day in the forest as post-exposure prophylaxis.

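### Primary endpoint timing is inconsistent: clinical malaria stops counting at day 28 although the visit can be on day 35 or later, Protocol 3.3 uses a different time origin from 6.6, and the windows for visits 2 and 3 have different upper limits

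*Protocol*

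**What the plan says.** **Timing of the primary PCR.** Protocol 3.3 assesses efficacy at "follow up visits 28 days (+/-7 days) after returning from the forest upon completing each course of prophylaxis" and refers to "Laboratory assessments of malaria infection at baseline and day 28 post forest". Section 6.6 asks participants to "return for a follow-up assessment any time from 28 to 35 days after commencing prophylaxis" and adds: "This will be regardless of the duration of their visit to the forest". The number of trips in the period does not matter either. Appendix 1 gives D28-35 for the first visit, counted from a D0 that carries randomisation and the first doses. The opening of Section 6 refers to Appendix 1 but then has participants "followed up every 28 days for up to 3 periods upon completion of a course of prophylaxis". Section 6.6.1 repeats 28-35 days without an anchor.

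**Later visits.** Section 6.6 sets "a second follow-up visit a further 28 to 35 days later", repeated once more. Appendix 1 gives D56-63 and D84-91. Participants who miss the window are seen as soon as possible (6.6).

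**Clinical malaria.** Protocol 5.4.1 counts cases "reported between day 0 and day 28". SAP 2.2 and 4.3 keep that cut-off. Yet at the visit 6.6 collects malaria tests and treatment over the whole preceding 28-35 days, and 3.3 records episodes at any time from enrolment to follow-up.

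The SAP speaks of 28-, 56- and 84-day results without giving an anchor, a window or a rule for samples taken outside it.

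**The concern.** A primary endpoint needs one time origin and one observation period. Here the two halves of the endpoint cover different periods. The PCR describes the participant on the day of the visit, whereas the clinical count closes on day 28. An episode that falls between the two and has been treated may leave no trace in either half, although the trial has recorded it.

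The origin of the PCR window also matters. Counted from return, sampling falls around the end of the four weeks of post-forest prophylaxis described in 6.5. Counted from first dose, it can fall earlier relative to exposure, and for a long stay before or soon after return. That changes how much time an infection has had to become detectable.

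The later windows matter because SAP 2.2 brings the Month 2 and Month 3 follow-ups into the primary endpoint. With two upper limits in force, whether a visit is on time depends on which page is read, in a trial where allocation is open.

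**Working it through.** **Inputs.** First visit on days 28-35 from first dose and later intervals of 28-35 days (6.6); D28-35, D56-63, D84-91 (Appendix 1); 28 +/-7 days after return, so 21-35 days (3.3); forest entry 0-3 days after enrolment (5.5.2, the 72-hour criterion); at least 10 days at risk per episode (9.1), taken here as a single stay; weekly dosing for four weeks after leaving the forest (6.5).

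**1. Clinical malaria cut-off.** If the visit is on day V, days 29 to V lie outside the clinical count: V - 28 days. Within the 6.6 window this runs from 28 - 28 = 0 to 35 - 28 = 7 days, so at most 7/35 = 20% of the days since first dose, and more for a late visit. This is a share of time, not of events. An example is an episode treated on day 30 with a negative PCR on day 34. It is not clinical malaria by day 28 and not a positive PCR, so it is no event under the SAP's composite. Under the Protocol's co-primary wording the clinical endpoint omits it whatever the PCR shows. SAP 2.2 applies the same day limits to each follow-up month without saying where day 0 restarts, so it does not clearly place the episode in the next period. A participant with no second visit has no next period.

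**2. Time origin.** With return on day r, 3.3 gives days r + 21 to r + 35.

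| Stay, entry day | Return | 3.3 window | Days shared with D28-35 |
|---|---|---|---|
| 7 days, day 0 | D7 | D28-42 | 8 (all) |
| 10 days, day 0 | D10 | D31-45 | 5 |
| 10 days, day 3 | D13 | D34-48 | 2 |
| 14 days, day 0 | D14 | D35-49 | 1 |
| 21 days, day 0 | D21 | D42-56 | 0 |

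There is no common day once r + 21 > 35, that is, once return is after day 14. For return by day 7 the 3.3 window contains all of D28-35.

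**3. Later windows.** Under 6.6, visit k falls on days 28k to 35k; Appendix 1 gives 28k to 28k + 7.

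| Visit | 6.6 | Appendix 1 | Extra days under 6.6 |
|---|---|---|---|
| 1 | D28-35 | D28-35 | 0 |
| 2 | D56-70 | D56-63 | 7 |
| 3 | D84-105 | D84-91 | 14 |

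The lower limits agree and the upper limits do not. If the first visit is anywhere in D28-35 and each later interval is 28 days, every visit meets Appendix 1: 0% fall outside. If every interval is 35 days, visits 2 and 3 fall on D70 and D105: 100% outside.

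The 112-day maximum in 6.6 shows the same slippage. It is reproduced with 28-day periods (3 x 28 + 28 = 112), whereas the 35-day end of the range stated in that sentence gives 3 x 35 + 28 = 133. Those figures also need reconciling; nothing here says which duration is intended.

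**The case against.** The strongest reply is that the operative text is clear for the primary visit. Section 6.6 and Appendix 1 agree on D28-35, Section 6 says procedures follow Appendix 1, and 3.3 is an overview under Background and Rationale. The opening of Section 6 is weak support for another anchor, since 6.5 uses the word course for the first three days of dosing. All of this stands: 3.3 is the outlier, and a reader who inferred that the day-28, 56 and 84 endpoints have incompatible definitions would go too far.

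A reader might also infer that 3.3 samples off drug and 6.6 on drug. For a 10-day stay from day 0 that is not so. Section 6.6 samples 28 - 10 = 18 to 35 - 10 = 25 days after return, which is also after exposure, and post-forest dosing can run to 10 + 28 = D38, inside the 3.3 window of D31-45. The contrast becomes sharp only for longer stays.

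A third inference is that visits obeying 6.6 would be dropped from the per-protocol set. No text says so. SAP 3.1 and 4.3 give no visit window, 6.6 accommodates late visits, the main analysis is by intention to treat, and SAP Table 2 reports by month.

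Finally, day 28 in the clinical endpoint may be only a nominal label for the first visit. That is possible, but the documents do not say it, and the literal cut-off is repeated in the SAP.

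**Conclusion.** The timing of the primary endpoint is inconsistent in three places and should be reconciled.

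- **Clinical cut-off.** This is the part that can change what is counted. It leaves up to 7 days uncovered for a visit inside the window, and more for a late one. How many episodes would be lost, and whether equally in both arms, is not known from the documents.
- **Time origin.** The conflict is between 3.3 and the two operative texts, which agree with each other. For a 10-day stay the windows share 5 to 2 days for entry on day 0 to 3, and none once return is after day 14. This rests on treating the planning minimum in 9.1 as one continuous stay; actual stays are not given.
- **Visits 2 and 3.** The Appendix 1 ranges are nested inside those of 6.6, so the fault is inconsistent upper limits. Anywhere from 0% to 100% of visits obeying 6.6 could fall outside Appendix 1. A single percentage is tempting: independent, uniform delays of 0-7 days would give 50% for visit 2 and 1 - 1/6 = 83% for visit 3. The documents supply no such distribution, and only participants planning another forest trip have these visits, so neither figure should be read as an estimate.

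**What to change.** 1. **Clinical malaria.** In Protocol 5.4.1 and SAP 2.2 and 4.3, count confirmed episodes from enrolment, or from the previous visit, to the actual PCR visit of that period. The data are already collected under 6.6. The small price is slightly variable follow-up time, which the planned Poisson or negative binomial model can handle by using actual time at risk.
2. **Anchor.** Bring 3.3 and the opening of Section 6 into line with the first-dose anchor of 6.6 and Appendix 1, and state that anchor in the SAP. It stays well defined when a participant makes several trips; return from the forest does not.
3. **Windows.** State one set of windows for the three visits in 6.6, Appendix 1 and the SAP, either cumulative from 6.6 or fixed from day 0. Add a rule for samples taken outside them, and say that a visit inside the reconciled window is not a per-protocol deviation.

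The cost is wording in the Protocol and SAP. No visit, sample or dose is added or changed.
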